taking the medication for decades. In particular, Hendricks and colleagues reported that phentermine did not induce physiological dependence or craving.³⁶ At low doses contained in Qsymia, phentermine works centrally through the release of norepinephrine in the hypothalamus, resulting in reduced appetite and decreased food consumption. There is weak activity on the dopamine transporter and even weaker activity on the serotonin transporter.³⁷ Common side effects of phentermine include dry mouth and insomnia, which typically improve over time with continued use. Phentermine has not been studied independently as an agent for treatment of BED or BN. In one small open label trial, patients were offered phentermine in combination with both fluoxetine and psychotherapy (CBT). Significant reductions in binge frequency as well as weight loss were found at post-treatment but weight regain and increases in binge eating were found with cessation of medications.³⁸ Five of 12 patients discontinued phentermine primarily due to perceived lack of efficacy after being on the drug over time. Without a control group, separation of the effects of medication from psychotherapy is not possible.

[figure not shown]
Topiramate was FDA-approved for the treatment of epilepsy in 1996 and for migraine prophylaxis in 2004. It has multiple mechanisms of action which are not fully understood. Its pharmacologic effects include blockade of voltage-gated sodium channels, enhancement of gamma-aminobutyrate activity (GABA), antagonism of glutamate receptors, and inhibition of carbonic anhydrase. It has been suggested that topiramate may have effects on insulin signaling and hypothalamic leptin as well as AMP-activated protein kinase (AMPK) signaling in peripheral tissues. ³⁹ Topiramate's exact mechanism of anorexic action is largely unknown, but its effects may be due to both appetite suppression and satiety enhancement. Topiramate has been shown to be effective in reducing binge eating in patients with both BED and BN. ¹⁰

[figure not shown]
However, the drop-out rates due to side effects in topiramate studies have been high (up to 50%). These side effects primarily include sedation, memory/concentration impairment and parasthesias.³⁵

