The study was reviewed and approved by the Institutional Review Board of Stanford University Medical Center. The research is being conducted in the Department of Psychiatry and Behavioral Sciences and is carefully monitored (protocol # 31390) by a Data Safety Monitoring Board at Stanford University. This is a randomized double-blinded placebo-controlled crossover trial totaling 34 weeks in length with ongoing enrollment of adults with BED (up to n = 15) and BN (up to n= 15). Patients are randomized to identical appearing placebo or Qsymia with 4 standard FDA-approved doses of phentermine/topiramate ER: 3.75mg/23mg; 7.5mg/46mg; 11.25mg/69 mg; and 15mg/92mg. The oral administration follows a weekly titration increase as follows: The four doses of Qsymia are titrated in a gradual fashion weekly over the course of four weeks, beginning with the lowest standard dose of phentermine/topiramate (3.75 mg/23 mg) up to the highest standard dose (15mg/92 mg) as tolerated. Each week of the 4-week ramp up period, the dose is increased to the next standard dose, provided no major side effects are reported. The final dose prescribed will be the minimum dose at which effects are seen and side effects are tolerable. Patients are randomized to 12 weeks of treatment with Qsymia or placebo, then a 2-week washout followed by a crossover of 12 weeks (total 26 weeks) and a final 8 weeks of follow-up while off medications, totaling 34 weeks (Figure 1). The washout period of two weeks was chosen to account for sufficient time to allow completion of at least five half lives, given a halflife in plasma of twenty hours for phentermine and sixty-five hours for topiramate. Per the protocol, subjects will be expected to attend 12 study visits spaced 2-4 weeks apart. Compensation in the form of giftcards of twenty US dollars will be given for completion of each assessment: post-treatment 1, post-treatment 2, follow-up 1 and 2 assessments. For participants who complete all four assessments, an additional twenty US dollars will be given.

Sample Size and Statistical Power

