Inclusion and exclusion criteria during the screening process will help to exclude patients who might suffer side effects from the treatment (e.g., low potassium) while assuring that those entered will have the appropriate diagnosis to possibly benefit from this treatment. At the first study visit, the study physician reviews all inclusion/exclusion criteria as well as all labs again. Any female with confirmed or intended pregnancy is informed and excluded due to potential teratogenicity. Women are counseled specifically that the extra risk of cleft lip and/or palate when taking topiramate during the first trimester is 1 in 500. Physician investigators involved in prescribing Qsymia have taken the REMS training program offered by Vivus (Campbell, CA) in an effort to reduce risk of teratogenicity for women of childbearing potential. The need for consistent use of effective contraception during treatment is encouraged. All participants are given information about Qsymia and the most common side effects at the top doses (e.g., tingling/parasthesias, constipation, dry mouth, abnormal taste, dizziness, insomnia, nausea, depression, blurred vision, low potassium, and angle closure glaucoma [less than 1 in 1000]). ⁴⁴

To improve the likelihood of safety during the trial, any patients with baseline potassium levels between 3.0-3.5 milli-equivalents/liter would be encouraged to ingest foods higher in potassium. To reduce the risk of side effects such as insomnia, patients are instructed to take Qsymia in the morning, with or without food. To reduce the risk of renal stones, parasthesias, or dry mouth, patients are instructed to drink 8 glasses of water per day. Patients are told to report any symptoms of blurred vision and/or eye pain. In such cases Qsymia is discontinued and patients are referred for intra-ocular pressure measurement within one day of symptom onset.

Measures

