Measures include demographic data, vital signs (including heart rate, blood pressure, weight), Eating Disorder Examination (EDE),⁴⁵ Eating Disorder Examination Questionnaire (EDE-Q),⁴⁶ Yale-Brown Obsessive Compulsive Scale for Binge Eating (YBOCS-BE),⁴⁷ Three Factor Eating Questionnaire (TFEQ),⁴⁸ Yale Food Addiction Scale (YFAS), ⁴⁹ Binge Eating Scale (BES),⁵⁰ and Patient Health Questionnaire (PHQ-9). ⁵¹ Major assessment points are scheduled prior to randomization (baseline 1), after 12 weeks of treatment (post-treatment 1), prior to the crossover (baseline 2), after the 12 week crossover (post-treatment 2), and after follow-up months 1 (follow-up 1) and 2 (follow-up 2). In addition, vital signs are recorded at each of the 12 medication visits. Weekly online binge trackers are used to record participants' self-reported binge and/or purge episodes.

The primary and secondary study efficacy outcomes are listed in Table 1.

Table 1. Finnary and secondary study enfeacy outcomes
Primary study outcome
Number of binge eating days per week from EDE (average over 28 days)
Secondary study outcomes
Number of binge eating episodes from EDE (average per 28 days)
Abstinence (no binge eating episodes) from EDE over past 28 days
Binge Eating Scale (BES)
Patient Health Questionnaire (PHQ-9)
Eating Disorder Examination Questionnaire (EDE-Q)
Dietary restraint subscale
Eating concern subscale
Weight concern subscale
Shape concern subscale
Global Score for all subscales
Three-Factor Eating Questionnaire (TFEQ)
Cognitive restraint of eating subscale
Disinhibition score subscale
Hunger score subscale
Yale-Brown Obsessive Compulsive Scale modified for binge eating (YBOCS-BE)
Yale Food Addiction Scale (YFAS)

Table 1. Primary and secondary study efficacy outcomes

Data Analysis Plan

The primary outcome measure will be the average number of binge eating days per week, as assessed by the EDE. Secondary outcome measures include the average number of binge eating episodes and percentage abstinence from binge eating. Throughout the study, weekly online binge trackers are used to record participants' binge and/or purge episodes per week per patient report. Vitals (weight, heart rate, blood pressure) and side effects will be assessed at each visit to ensure safety. See Table 2. In addition, any treatment-emergent adverse events will be recorded.

Table 2. Assessment Schedule

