Measures	Baseline1 (Wk0)	Med Visit 1 (Wk0)	Med Visit 2 (Wk2)	Med Visit 3 (Wk4)	Med Visit 4 (Wk8)	Med Visit 5 PT1 (Wk12)	Med Visit 6 BL2 (Wk14)	Med Visit 7 (Wk16)	Med Visit 8 (Wk18)	Med Visit 9 (Wk22)	Med Visit 10 PT2 (Wk26)	Follow Up Med Visit 11 (Wk30)	Follow Up Med Visit 12 (Wk34)
Informed Consent	Х												
Demographics	Х												
Vitals (Weight/HR/BP) & Side Effects	х	Х	Х	Х	Х	Х	Х	X	Х	Х	Х	X	Х
EDE	Х					Х	Х				Х		
BES	Х					Х	Х				Х		
PHQ-9	Х					Х	Х				Х		
EDE-Q	Х					Х	Х				Х		

Study Protocol And Rationale Phentermine-Topiramate ER

TFEQ	Х			Х	Х		Х	
YBOCS-BE	Х			Х	Х		Х	
YFAS	Х			Х	Х		Х	

*Abbreviation Key: Eating Disorder Examination (EDE), Binge Eating Scale (BES), Patient Health Questionnaire (PHQ-9), Eating Disorder Examination Questionnaire (EDE-Q), Three Factor Eating Questionnaire (TFEQ), Yale-Brown Obsessive Compulsive Scale for Binge Eating (YBOCS-BE), and Yale Food Addiction (YFAS), Baseline Assessment (BL1, BL2), Post-Treatment Assessment (PT1, PT2). Crossover occurs at Medication Visit 6 with twoweek washout prior.

Primary and secondary study outcomes will be compared using intention-to-treat (ITT) analysis for all randomized patients. Mixed-effects models with fixed effects for treatment, follow-up period, treatment by period (interaction representing carry-over effect), and eating disorder diagnosis (used to stratify randomization) will be used to estimate the treatment effect. Mixedeffects models include subject-level random effects to account for repeated measurements within subjects. Non-significant treatment by period interaction ($p \ge 0.05$) will be removed from the model before estimating the final treatment effect. In the case of a significant treatment by period interaction (p < 0.05) the analysis will revert to that of a standard parallel arm randomized trial using data from the first period only. A p-value of less than 0.05 is considered statistically significant and the Kenward-Roger degrees of freedom approximation will be used in tests of significance from mixed models.

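### Two of each patient's three active-drug dose increases, including the one to 15/92 mg, have no scheduled side-effect check; separately, the secondary total-drug analysis can be confounded because dose may follow response

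*Combined protocol and SAP*

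**What the plan says.** **Titration.** Methods, Procedure gives four strengths of phentermine/topiramate ER (3.75/23, 7.5/46, 11.25/69 and 15/92 mg), moved up weekly over four weeks. The condition for each move is that "the dose is increased to the next standard dose, provided no major side effects are reported". The same section sets the final dose as the lowest one that shows an effect and is tolerated.

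**Visits and side effects.** Methods, Procedure says that "subjects will be expected to attend 12 study visits spaced 2-4 weeks apart". The Data Analysis Plan says that "side effects will be assessed at each visit to ensure safety". In Table 2 the visits that start and cover the ramp-up are at weeks 0, 2 and 4 in period 1 and weeks 14, 16 and 18 in period 2.

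**Contact between visits.** Measures describes a weekly online tracker for "self-reported binge and/or purge episodes"; no side-effect item is mentioned. Safety/Tolerability adds: "Patients are told to report any symptoms of blurred vision and/or eye pain".

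**Dose and response.** The Discussion lets the physician adjust drug or placebo on efficacy and on side effects. Its example is a patient who is doing well on a lower dose but has side effects; that patient is held, and raised only if symptoms return. The Data Analysis Plan lists a secondary analysis with the total amount of drug taken as an exposure variable.

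**The concern.** A rule that stops escalation when a major side effect is reported protects the patient only if someone knows about the side effect before the next step. Where no enquiry is scheduled, silence is treated as tolerance. The plan's own rationale makes this matter: tolerability is the stated limitation of topiramate, and the Discussion says the protocol was built to keep risk as low as possible.

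The second issue is analytic. If a patient who responds early is kept on a low dose while a non-responder is taken to the top, total drug taken is partly a consequence of outcome. Regressing outcome on it can then make more drug look harmful even when the drug does nothing.

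**Working it through.** **1. The stated schedule reproduces.** Table 2 gives medication visits at weeks 0, 2, 4, 8, 12, 14, 16, 18, 22, 26, 30 and 34. That is 12 visits, with gaps of 2, 2, 4, 4, 2, 2, 2, 4, 4, 4 and 4 weeks, as Methods, Procedure says.

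**2. Steps against visits.** Four strengths give three increases per period. With the lowest dose starting at week 0 and, after crossover at Medication Visit 6, at week 14, the increases fall as follows.

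| Week | Step to (mg) | Visit that week? |
|---|---|---|
| 1 | 7.5/46 | no |
| 2 | 11.25/69 | yes |
| 3 | 15/92 | no |
| 15 | 7.5/46 | no |
| 16 | 11.25/69 | yes |
| 17 | 15/92 | no |

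Four of six steps have no visit. Each patient takes active drug in one period only, so the active count is 2 of 3, including the single active step to 15/92 mg. The ramp-up visits see the patient after a week on the 46 mg and 92 mg topiramate strengths; the weeks on 23 mg and 69 mg end in an increase with no scheduled enquiry. Every unchecked step is followed by a visit one week later.

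*Sensitivity to the start date.* If the first dose began a week later, the steps would fall at weeks 2, 3, 4, 16, 17 and 18, and only weeks 3 and 17 (to 11.25/69 mg) would lack a visit. That fits poorly with four doses in four weeks inside a 12-week period.

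**3. How many steps.** Upper limit, with nobody held: 30 patients × 3 = 90 active steps, of which 30 × 2 = 60 have no visit. With 24 patients, 24 × 2 = 48 of 24 × 3 = 72. The documents give no rate of major side effects per dose week, so I assume 1%, 5% or 10%. For 60 steps: 60 × 0.01 = 0.6, 60 × 0.05 = 3, 60 × 0.10 = 6. For 48 steps: 0.48, 2.4 and 4.8. These are increases that would follow a major side effect, before subtracting those reported spontaneously.

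**4. Total drug depends on where titration stops.** Topiramate over 12 weeks is 7 × the sum of the weekly daily doses:

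- held at 23 mg: 7 × 12 × 23 = 1,932 mg
- held at 46 mg: 7 × (23 + 11 × 46) = 3,703 mg
- held at 69 mg: 7 × (23 + 46 + 10 × 69) = 5,313 mg
- taken to 92 mg: 7 × (23 + 46 + 69 + 9 × 92) = 6,762 mg

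The first three are 29%, 55% and 79% of the last.

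**5. Direction of the bias.** An illustration among patients on active drug, with every input assumed: baseline 4 (SD 1) binge days a week, mean response 1 (SD 1), titration stopped at a reduction of 1 day or more, noise SD 0.5. The true extra benefit from lowest to highest dose was set between 0 and 1 day. With dose assigned at random, the slope of outcome on total drug ran from 0.00 to -0.20 binge days a week per gram. With response-guided dosing it ran from +0.35 to +0.20, so the sign is wrong or spurious.

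**6. Dependence on the hold rule.** A simulation with no drug effect (24 patients, nominal 5% test, random-intercept model on change from baseline) was run under three rules. It assumed improvement of mean 3.3, SD 2.0 days per period (the placebo figure quoted from a lisdexamfetamine trial in binge eating disorder, ± read as SD), within-patient correlation 0.5, half the response visible in week 1 and all by week 4, tracker noise SD 1 day, and a 5% side-effect hold per step.

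- Responders always escalated: rejection 4.9%.
- The Discussion's example (held only with response and side effects, 20–50% having side effects): 5.7–8.4%.
- Response alone holds the dose, at 1, 2 or 3 fewer binge days: 35.2%, 26.9% and 13.5%. Varying how early response shows moves the 2-day figure between 13.8% and 37.8%.

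The intention-to-treat test rejected in 4.6–5.4% throughout.

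**The case against.** **Monitoring.** A reader might infer that patients are escalated with no safety net. The documents do not support that. Participants receive information on side effects and are told to report eye symptoms, intolerable effects lead to a lower dose, adverse events are recorded, and a data safety monitoring board oversees the study. Major side effects are also the ones patients are most likely to volunteer. The paper is a published account of a protocol, so undescribed contacts between visits may exist. All of this stands; the narrower point that no routine enquiry is scheduled before those steps also stands.

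**The background drop-out figure.** The statement that "drop-out rates due to side effects in topiramate studies have been high (up to 50" per cent) should not be carried over to this trial. The BED – Current Treatment section gives 150–600 mg for the randomized topiramate studies in binge eating disorder, whereas the maximum here is 92 mg ER, combined with a drug expected to offset sedation and cognitive effects.

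**The count.** Four of six includes placebo steps, and repeat titration in period 2 is inferred from the blinded crossover rather than stated. The fair figure is 2 of 3 active steps per patient.

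**The exposure analysis.** It is one clause about a secondary analysis, with no model, metric or causal claim given. The larger rejection rates need response alone to hold the dose, plus inputs that the documents do not supply. That objection is right about size, and it leaves the direction of the problem intact.

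**Conclusion.** The point holds in a limited form. Each patient has 2 of 3 active-drug increases, including the step to 15/92 mg, without a scheduled side-effect check. This rests on the first dose being taken at weeks 0 and 14 and on side effects being sought only at visits, as the documents describe. The gap before the next visit is one week. It is worth closing because the remedy is cheap.

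The total-drug analysis can be confounded, with lower exposure marking improvement. How much depends on how often responders are held, and no single figure can be taken from the documents. A reader might infer that flexible dosing also biases the main result. It does not: the primary analysis compares drug with placebo as randomized, and dose adjustment is part of the treatment being compared.

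A reader might also infer that responders without side effects are meant to keep escalating, since the weekly condition names only side effects. The minimum-effective-dose rule in Methods, Procedure points the other way.

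**What to change.** 1. Add one side-effect question to the existing weekly online tracker. The blinded physician reads it before the steps at weeks 1, 3, 15 and 17, and a phone call replaces it if the tracker is not completed. The major-side-effect condition stays as it is. If such a contact already takes place, describe it in the protocol. Scheduled coverage goes from 2 of 6 steps to 6 of 6.
2. Report total drug received descriptively, or label the analysis non-causal because dose can follow response.

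Do not add a rule that responders without side effects continue upward. It would conflict with the minimum-effective-dose rule and raise exposure in patients who are already doing well.

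Cost: one question, up to 4 readings per patient (4 × 30 = 120), some phone calls, a short amendment, an occasional delayed step, and no causal exposure–response claim. No extra visits or patients are needed, and the sample size of 24 inflated to 30 does not change.

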Adults age 18 to 60 are being recruited via online advertisements, newspaper, flyers, and referrals from local clinics within the community since July 2015. Inclusion criteria are: (a) meet DSM-5 criteria for BN or BED refractory to prior treatment, (b) have a BMI of 21 or greater, (c) if female with child-bearing potential, must have an initial negative pregnancy test and have adequate birth control measures, (d) must be medically stable with no new diagnoses (medical, surgical, or psychiatric) within the past 6 months, (e) must be able to comply with all 12 study visits, treatment plans, and blood draws at Stanford. Exclusion criteria include: (a) any patient with bipolar disorder or schizophrenia, any patient taking a mood stabilizer or antipsychotic medication within the past 3 months of enrollment, or any patient on an unstable SSRI dose (change in dosage over the prior 30 days), (b) any patient with current or past history of anorexia nervosa (including BMI < 17.5), (c) any history of prior (within 30 days) use of over the counter weight-reducing agents or herbal preparations, (d) any prescription weight loss medication within 3 months of enrollment, (e) any patient who started a psychological weight-loss intervention (e.g. Weight Watchers, Jenny Craig) within the prior month or if started over a month and achieved weight loss, (If no weight loss was achieved in over a month, eligibility was considered provided willingness to discontinue the weight intervention) (f) currently receiving

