therapy with a psychostimulant or used a psychostimulant within past 6 months of enrollment, (g) any known sensitivity to phentermine or topiramate, (h) change in thyroid, psychiatric (e.g., antidepressant), or blood pressure medications within the past one month, (i) on a potassiumwasting diuretic, (i) on a carbonic anhydrase inhibitor such as zonisamide or acetazolamide, (k) on insulin or an insulin secretagogue, (1) liver enzymes at baseline greater than three times the upper limit of normal, (m) any baseline potassium of less than 3.0 milliEquivalents/liter, (n) abnormal baseline Thyroid Stimulating Hormone (TSH) greater than 1.5 times the upper limit of normal, (o) any patient unwilling or expressing uncertainty about being able to refrain from daily alcohol use (even if at moderate levels) or illegal drugs while taking the study medication, including medical marijuana, (p) any recent history of suspected substance abuse or dependence, (q) history of misuse of a stimulant, (r) current suicidal ideation or baseline Patient Health Questionnaire (PHQ-9) score of 20 or greater, (s) history of nephrolithiasis, (t) is pregnant or who is planning to become pregnant during the study period, (u) unable to identify a primary care physician, (v) history of cardiovascular disease (i.e. recent history of myocardial infarction, stroke, shortness of breath, chest pain) that could increase vulnerability to the sympathomimetic effects of a stimulant-like drug.

Screening/Enrollment

Eligibility is assessed via an initial telephone screen to determine whether DSM criteria for BED or BN are met and whether any inclusion/exclusion criteria as detailed are/are not satisfied. Those who do not meet criteria are provided with a referral list for treatment/care. Those who meet criteria on initial screening are asked to complete baseline assessments, including labs and written informed consent, prior to invitation for an in-person clinical interview. The assessments are completed again after treatment in the first medication group, at baseline 2 prior to crossing over to the second medication group, and then after completion of the second medication group. Labs completed at baseline include complete blood count, complete metabolic panel, TSH, and if female, a pregnancy test. At study physician's discretion, additional labs may be ordered during the study as clinically appropriate.

Safety/Tolerability

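### Low potassium is a named side effect, but no potassium measurement after baseline is explicitly scheduled, and no reading of the plan gives one during titration

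*Combined protocol and SAP*

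**What the plan says.** **The risk is recognised.** Safety/Tolerability includes in its list of the most common side effects at the top doses: "insomnia, nausea, depression, blurred vision, low potassium, and angle closure glaucoma". The same section uses low potassium as its example of what screening should guard against. The exclusion criteria bar "any baseline potassium of less than 3.0 milliEquivalents/liter", and also bar patients on a potassium-wasting diuretic or a carbonic anhydrase inhibitor. Qsymia And Rationale For Use gives carbonic anhydrase inhibition as one of topiramate's own effects. For patients just above the entry limit, Safety/Tolerability says "any patients with baseline potassium levels between 3.0-3.5 milli-equivalents/liter would be encouraged to ingest foods higher in potassium", and mentions no repeat value.

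**The laboratory text.** Screening/Enrollment says that candidates are "asked to complete baseline assessments, including labs and written informed consent". The next sentence says the assessments are done again after the first medication period, at baseline 2 and after the second medication period. Then comes "Labs completed at baseline include complete blood count, complete metabolic panel, TSH, and if female, a pregnancy test", followed by "At study physician's discretion, additional labs may be ordered during the study as clinically appropriate". Inclusion criterion (e) says that a participant "must be able to comply with all 12 study visits, treatment plans, and blood draws at Stanford", without giving the number or timing of the draws.

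**The schedule.** The Measures section names vital signs, the EDE and the questionnaires, but no laboratory test. The Data Analysis Plan puts vitals and side effects at each visit. Table 2 has no laboratory row.

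**The concern.** The potassium criterion describes a participant on the day of the baseline sample. After that, the dose rises weekly over four weeks as long as no major side effect is reported, and active dosing continues to 12 weeks. A site could follow the written plan exactly and never measure potassium on drug.

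Two things are at stake:

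- **Participants.** Someone admitted at 3.0-3.5 mEq/L has no explicitly scheduled value to show whether the dietary advice worked. Participants with BN may also have behaviours that the protocol itself counts as compensatory, such as vomiting or laxative or diuretic misuse.
- **Safety data.** The abstract makes safety an aim of the trial. Laboratory tests ordered only at discretion would give a selected set of values, without a systematic drug-placebo comparison for a risk the protocol names.

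**Working it through.** The plan states no figure on this point, so there is none to reproduce. The check counts planned potassium values under each reading of Screening/Enrollment.

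**Inputs**

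- Timeline (Procedure): 12 weeks, 2 weeks washout, 12 weeks, 8 weeks follow-up. 12 + 2 + 12 + 8 = 34 weeks. Dosing takes 12 + 12 = 24 weeks, of which 12 are active for each participant.
- Titration (Procedure): the first four weeks of a period, so weeks 0-4 or weeks 14-18.
- Repeat times named in Screening/Enrollment, placed on Table 2: week 12 (post-treatment 1), week 14 (baseline 2), week 26 (post-treatment 2).
- Half-lives (Procedure): 20 h for phentermine, 65 h for topiramate. 5 × 65 = 325 h, and 325 / 24 = 13.5 days, which is within the 14-day washout. A week-14 sample therefore counts as off drug.

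**Count per participant**

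| Time | Drug-first | Placebo-first | Labs at baseline only | Labs repeated |
|---|---|---|---|---|
| Baseline | before drug | before drug | 1 | 1 |
| Week 12 | on drug | on placebo | 0 | 1 |
| Week 14 | after washout | after placebo and washout | 0 | 1 |
| Week 26 | on placebo | on drug | 0 | 1 |
| **On-drug values** | | | **0** | **1 in either sequence** |

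On the repeated reading, the one on-drug value falls at the end of the active period. On both readings the count is 0 during titration and 0 before the end of the 12 active weeks.

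**Age of the baseline value, baseline-only reading.** In the placebo-first sequence the single value is at least 12 + 2 = 14 weeks old at the first active dose, and about 14 + 12 = 26 weeks old or more when active dosing ends. On the repeated reading this does not arise, because a week-14 value would exist.

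**Which reading fits better**

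- *For baseline only:* the panel sentence names baseline alone, and any further labs are called additional and left to discretion. Written consent stands in the same list as labs, and Table 2 does not repeat it. The three repeat times are exactly those at which Table 2 marks the EDE and the questionnaires.
- *For repetition:* labs are expressly among the assessments that the next sentence says are done again, and inclusion criterion (e) speaks of blood draws in the plural.
- *Neutral:* Table 2 omits the baseline labs too, although these are certainly done, so its silence does not show that later labs are unplanned.

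The baseline-only reading is the more natural one, but the text does not settle it.

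**The case against.** A reader might infer that potassium is definitely measured once and that no participant has a planned value on drug. The documents do not support that as fact. Read literally, Screening/Enrollment repeats the labs at weeks 12, 14 and 26. That would give one value on drug, one on placebo and one after washout, and the point about an old baseline value would fall away. This part of the objection stands, so the count has to be given as 0 or 1.

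The plan also has other safeguards: side effects asked at every visit, adverse-event recording, weekly online trackers of binge and/or purge episodes, dose adjustment for side effects, a required primary care physician, oversight by a Data Safety Monitoring Board, and discretionary labs. A tracker report could well prompt a blood test. These safeguards are real, but none of them is a scheduled potassium measurement.

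Three further inferences go beyond the text:

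- *All participants with BN purge.* The Introduction gives vomiting and laxative or diuretic misuse as examples, beside exercise and fasting. The number who purge is not given.
- *A fall in potassium would go unnoticed.* The documents do not say whether it would cause symptoms, and they give no frequency for it.
- *The 3.0 and 3.5 limits should guide care on treatment.* The documents apply them to baseline values only.

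**Conclusion.** The concern holds in a limited form. No potassium measurement after baseline is explicitly scheduled, and the laboratory text can be read in two ways. Planned on-drug values per participant are 0 on the more natural reading and 1 on the other. The finding that does not depend on the reading is that none is planned during the four-week titration or before the end of the 12-week active period.

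This counts planned tests and is not an estimate of risk: the documents give neither the frequency of low potassium nor the number of participants at 3.0-3.5 mEq/L. It assumes that the complete metabolic panel is the source of the potassium value and that the repeat times correspond to weeks 12, 14 and 26. Confidence is moderate because of the ambiguous wording. The plan should be changed, since the protocol names the risk and the change is small.

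**What to change.** 1. Reconcile the laboratory statements in Participants: Inclusion/Exclusion Criteria, Screening/Enrollment and Safety/Tolerability with Table 2. It should be clear whether labs belong to the repeated assessments and which draws criterion (e) refers to.
2. Add a laboratory row to Table 2, with the baseline sample marked, that schedules the metabolic panel already used at baseline at existing visits. Use the same schedule in both periods, so that every participant has an on-drug value and a placebo value and the timing does not reveal the allocation. The row should state whether titration is covered. Table 2 already has visits at weeks 2 and 4 and at weeks 16 and 18.
3. Leave the exact timing, and any response to a low value, to the sponsor and its monitoring board. No threshold or dispensing rule is proposed here.

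The cost is an amendment to the text and the table, modest laboratory expense, and venepuncture at visits already planned, in participants who must already accept blood draws. No new visit is needed.
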